9.6.2 Bone Turnover Markers

Actual values and percent changes from baseline in each parameter (P1NP and sCTX) will be descriptively summarized for each dose cohort at each visit. **Graphs depicting**

summary statistics (change or percent change from baseline) for each parameter over time will be provided. The PD analysis set will be used to for the analyses.

9.6.3 Vital Signs

Vital signs will be reviewed for each subject. Depending on the size and scope of changes, summaries of vital sign data over time and/or changes from baseline over time may be provided. The safety analysis set will be used to for the analyses.

9.6.4 ECG

ECG data will be listed and reviewed for each subject. Depending on the size and scope of changes, summaries of ECG data over time and/or changes from baseline over time may be provided.

9.6.5 Physical Examinations

Height and weight data will be reviewed for each subject. Individual subject results will be examined in relation to baseline recordings. Depending on the size and scope of changes in data, summaries of physical examinations data over time and/or changes from baseline may be provided.

9.6.6 Safety Laboratory Tests

Actual values and changes from baseline in each parameter will be descriptively summarized each dose cohort at each visit. For serum calcium, phosphorous, and magnesium, the percent change from baseline also will be provided. All laboratory analyses will be based on the safety analysis set.

Graphs showing central tendency and dispersion of the absolute values and percent changes from baseline by visit will also be provided for the following laboratory parameters: calcium corrected by albumin, phosphorus and alkaline phosphatase.

Laboratory: Chemistry	Laboratory: Hematology
albumin	red blood cells
alkaline phosphatase (ALP)	Hemoglobin
ALT (SGOT)	Hematocrit
AST (SGPT)	mean corpuscular volume (MCV)
bicarbonate (HCO3)	mean corpuscular hemoglobin (MCH)
direct bilirubin	mean corpuscular hemoglobin concentration
total bilirubin	(MCHC)
blood urea nitrogen	platelet count
creatinine	white blood cells
creatine kinase	 total neutrophils
chloride	• eosinophils
magnesium	• basophils
phosphorous	Iymphocytes
potassium	• monocytes
Sodium	
total protein	
glucose	
25-OH vitamin D	
iPTH	
calcium	
albumin-corrected calcium	

Table 9-1. Safety Laboratory Test Panel

Drug-induced liver injury will be assessed by evaluating subjects for Hy's Law. Hy's law laboratory criteria are defined as aspartate transaminase or alanine transaminase > 3 times upper limit of normal (ULN), total bilirubin > 2 times ULN, and alkaline phosphatase < 2 times ULN assessed within 7 days.

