Proof of biological activity for romosozumab was established in a first-in-human, ascending-single-dose study in healthy males and postmenopausal females, an ascending-multiple-dose study in healthy males and postmenopausal females with low bone mass and a phase 2 dose-ranging study in postmenopausal females with low bone mass. In all studies, treatment with romosozumab was generally well tolerated and resulted in a transient increase of the bone formation markers procollagen type I N-terminal propeptide (P1NP), osteocalcin (OC), and bone-specific alkaline phosphatase (BSAP), and a decrease in the bone resorption marker serum type I collagen Ctelopeptide (sCTX) (McClung et al, 2014; Padhi et al, 2011; Padhi et al, 2014). Increases in BMD at the lumbar spine, total hip and femoral neck were also demonstrated by dual-energy X-ray absorptiometry (DXA) and Quantitative Computed Tomography (QCT) (Cosman et al, 2016; Graeff et al, 2015; Langdahl et al, 2017; McClung et al, 2014; Padhi et al, 2011; Padhi et al, 2014; Saag et al, 2017). With enduring gains in bone mass, the risk for patients to experience an osteoporotic fracture can be lessened, as demonstrated during the romosozumab phase 3 program as described below.

Study 20080289 compared romosozumab 210 mg QM with teriparatide 20 μ g daily for 12 months in women with postmenopausal osteoporosis (PMO) at high risk for fracture and transitioning from bisphosphonate therapy. A statistically significant difference of 3.2% (95% CI 2.7 to 3.8; p<0.0001) in favor of romosozumab in the percent change of total hip BMD (measured by DXA) through month 12 was observed (Langdahl et al, 2017).

In Study 20110174 of men with osteoporosis, subjects receiving romosozumab 210 mg QM had a statistically significant increase in BMD at the lumbar spine, femoral neck, and total hip at 6 and 12 months, compared with those receiving placebo. At month 12, subjects who received romosozumab demonstrated a mean percent increase in BMD at the lumbar spine from baseline of 12.1% (least squares mean) vs 1.2% for the placebo group. At the total hip and femoral neck, subjects who received romosozumab demonstrated a mean (least squares mean) percent increase in BMD from baseline of 2.5% vs - 0.5% for the placebo group, and 2.2% vs -0.2% for the placebo group, respectively.

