6.4 Hepatotoxicity Stopping and Rechallenge Rules

Subjects with abnormal hepatic laboratory values (ie, alkaline phosphatase [ALP], AST, ALT, total bilirubin) and/or international normalized ratio (INR) and/or signs/symptoms of hepatitis (as described below) may meet the criteria for withholding or permanent discontinuation of Amgen IP or other protocol-required therapies as specified in the Guidance for Industry Drug-induced Liver Injury: Premarketing Clinical Evaluation, July 2009.

6.4.1 Criteria for Permanent Withholding of Amgen Investigational Product and Other Protocol-required Therapies due to Potential Hepatotoxicity

Investigational product and other protocol-required therapies, as appropriate, should be discontinued permanently and the subject should be followed according to the recommendation in Appendix A (Additional Safety Assessment Information) for possible drug-induced liver injury (DILI), if all the criteria below are met:

- Total bilirubin > 2x upper limit of normal (ULN) or INR > 1.5
- AND increased AST or ALT from the relevant baseline value as specified below:

Baseline AST or ALT value	AST or ALT elevation				
< ULN	> 3x ULN				

- AND no other cause for the combination of the above laboratory abnormalities is immediately apparent; important alternative causes for elevated AST/ALT and/or total bilirubin values include, but are not limited to:
 - Hepatobiliary tract disease
 - Infectious hepatitis (eg, hepatitis A/B/C/D/E, Epstein-Barr Virus, cytomegalovirus, herpes simplex virus, varicella, toxoplasmosis, and parvovirus)
 - Right sided heart failure, hypotension or any cause of hypoxia to the liver causing ischemia.
 - Exposure to hepatotoxic agents/drugs or hepatotoxins, including herbal and dietary supplements, plants and mushrooms
 - Heritable disorders causing impaired glucuronidation (eg, Gilbert's Syndrome, Crigler-Najjar syndrome) and drugs that inhibit bilirubin glucuronidation (eg, indinavir, atazanavir)
 - Alpha-one antitrypsin deficiency
 - Alcoholic hepatitis
 - Autoimmune hepatitis
 - Wilson's disease and hemochromatosis
 - Nonalcoholic fatty liver disease including steatohepatitis (NASH)
 - o Non-hepatic causes (eg, rhabdomylosis, hemolysis)

6.4.2 Criteria for Conditional Withholding of Amgen Investigational Product and Other Protocol-required Therapies due to Potential Hepatotoxicity

The following rules are recommended for withholding of IP and other protocol-required therapies:

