• Elevation of either AST or ALT according to the following schedule:

Baseline AST or ALT	AST or ALT Elevation
value	AST OF ALT Elevation
Any	> 8x ULN at any time
Any	$>$ 5x ULN but $<$ 8x ULN for \ge 2 weeks
Any	> 5x ULN but < 8x ULN and unable to adhere to protocol enhanced monitoring schedule
Any	> 3x ULN with clinical signs or symptoms that are consistent with hepatitis (such as right upper quadrant pain/tenderness, fever, nausea, vomiting, and jaundice).

- OR: TBIL > 3x ULN at any time
- OR: ALP > 8x ULN at any time

Investigational product and other protocol-required therapies, as appropriate, should be withheld pending investigation into alternative causes of DILI. If IP is withheld, the subject is to be followed according to recommendation in Appendix A for possible DILI. Rechallenge may be considered if an alternative cause for impaired liver tests (ALT, AST, ALP) and/or elevated total bilirubin is discovered and the laboratory abnormalities resolve to normal or baseline.

6.4.3 Criteria for Rechallenge of Amgen Investigational Product and Other Protocol-required Therapies After Potential Hepatotoxicity

The decision to rechallenge the subject should be discussed and agreed upon unanimously by the subject, the subject's legally acceptable representative, investigator, and Amgen.

If signs or symptoms recur with rechallenge, then IP and other protocol-required therapies, as appropriate should be permanently discontinued. Subjects who clearly meet the criteria for permanent discontinuation (as described in Section 6.4.1) should never be rechallenged.

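### The SAP's only drug-induced liver injury evaluation requires ALP < 2x ULN, which bone can breach in this trial, so it may under-count subjects who meet the protocol's own laboratory criteria

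*SAP*

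**What the plan says.** SAP section 9.6.6 states: "Drug-induced liver injury will be assessed by evaluating subjects for Hy's Law". The criteria are "aspartate transaminase or alanine transaminase > 3 times upper limit of normal (ULN), total bilirubin > 2 times ULN", together with "alkaline phosphatase < 2 times ULN assessed within 7 days". There is no INR alternative.

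Protocol section 6.4.1, on permanent withholding for possible drug-induced liver injury, requires "Total bilirubin > 2x upper limit of normal (ULN) or INR > 1.5", a transaminase rise above 3x ULN (its table lists a baseline below ULN), "AND no other cause for the combination of the above laboratory abnormalities is immediately apparent". ALP is not among the conditions. Appendix A uses the section 6.4 criteria to define which concurrent transaminase and bilirubin and/or INR elevations must be reported as serious adverse events within 24 hours, again without reference to ALP. ALP taken alone appears only in section 6.4.2, at "ALP > 8x ULN at any time".

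On the drug, protocol section 2.2 says that treatment in the early adult studies "resulted in a transient increase of the bone formation markers procollagen type I N-terminal propeptide (P1NP), osteocalcin (OC), and bone-specific alkaline phosphatase (BSAP"). Section 2.1 describes increased bone turnover in osteogenesis imperfecta. Exclusion criterion 220 limits AST, ALT and total bilirubin to 1.5x ULN at entry but sets no limit on ALP.

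**The concern.** The chemistry panel measures total ALP, which does not separate liver from bone. The SAP does not say why it sets the ceiling. If it is there to set aside cholestatic patterns, it works only when a raised ALP points to the liver. Here a raised ALP may instead reflect growth, the disease or the drug's intended effect on bone.

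A child whose ALP is at or above 2x ULN for any of these reasons cannot be counted under Hy's Law, however high the transaminases and bilirubin go. A child who enters at that level and stays there can never be counted.

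At stake is the consistency of the liver safety report. It could state that no subject met Hy's Law while the serious adverse event tables show a subject who met the protocol's criteria for potential drug-induced liver injury. The other planned laboratory output does not clearly close the gap. The grade-shift tables were dropped (SAP section 10), and the summaries by cohort and visit treat each parameter separately, so they do not link transaminases, bilirubin and INR within a subject.

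**Working it through.** The plan gives no figure to reproduce, so the check compares the two definitions.

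**Definitions side by side**

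| Element | SAP 9.6.6 | Protocol 6.4.1 |
|---|---|---|
| AST or ALT | > 3x ULN, any baseline | > 3x ULN, baseline < ULN |
| Total bilirubin | > 2x ULN required | > 2x ULN, or INR > 1.5 |
| INR | not used | > 1.5 accepted in place of bilirubin |
| ALP | < 2x ULN required | no condition |
| Other causes | no condition | none immediately apparent |
| Timing | within 7 days | not stated in 6.4.1 |

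**Step 1: count the combinations.** Take AST/ALT > 3x ULN (yes/no), bilirubin > 2x ULN (yes/no), INR > 1.5 (yes/no) and ALP in three bands (< 2x, 2x to 8x, > 8x ULN). That gives 2 × 2 × 2 × 3 = 24 combinations. Assume baseline AST/ALT below ULN, no other apparent cause, and all results within the time window.

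- Protocol 6.4.1 is met when AST/ALT is yes and bilirubin or INR is yes: 1 × 3 × 3 = 9.
- SAP 9.6.6 is met when AST/ALT is yes, bilirubin is yes, INR is either, and ALP is < 2x ULN: 1 × 1 × 2 × 1 = 2. Both are among the nine.
- Not captured by the SAP: 9 − 2 = 7. Four have bilirubin > 2x ULN with ALP at or above 2x ULN (2 INR states × 2 ALP bands). Three qualify through INR only (3 ALP bands).

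**Step 2: effect of changing the definition.**

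| Definition | Combinations not captured, of 9 |
|---|---|
| As written | 7 |
| ALP condition dropped, no INR | 3 |
| INR > 1.5 added, ALP condition kept | 6 |
| Both changes | 0 |

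These figures count logical combinations. They are not proportions of patients.

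**Step 3: how large a bone effect would be needed.** Let b be baseline total ALP in multiples of ULN, s the bone share of total ALP, and r the relative rise in the bone fraction. Then total ALP = b(1 + s·r). It reaches 2x ULN when r = (2 − b)/(b·s). The documents give neither b nor s, so both are assumptions, with s from 0.5 to 0.9.

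| Assumed b | r at s = 0.5 | r at s = 0.9 |
|---|---|---|
| 0.8 | 1.2/0.40 = 300% | 1.2/0.72 = 167% |
| 1.0 | 1.0/0.50 = 200% | 1.0/0.90 = 111% |
| 1.5 | 0.5/0.75 = 67% | 0.5/1.35 = 37% |
| 2.0 | 0% | 0% |

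From a baseline within the reference range the bone fraction must at least double. From a raised baseline, which eligibility permits, a modest rise or none is enough.

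**Step 4: availability of INR.** INR is absent from the protocol's chemistry panel (Table 7) and from SAP Table 9-1. It appears in the close-observation work-up in Appendix A, which applies to subjects with AST or ALT > 3x ULN, among others. It should therefore exist for the subjects who matter, but not as scheduled data.

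**The case against.** A reader might infer that real liver-injury cases will be missed. The documents do not support this. Appendix A makes a qualifying case a serious adverse event within 24 hours, before the cause has been investigated and whatever the ALP. SAP section 9.6.1 tabulates serious adverse events and events leading to withdrawal of the product, and lists every treatment-emergent event by subject. With four subjects per cohort, the minimum and maximum at each visit would also expose an extreme AST, ALT or bilirubin value. What can be lost is the subject's place in the Hy's Law evaluation.

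A reader might also infer an undeclared departure from the protocol, since SAP section 10 does not mention the difference. That is not supported either. Protocol section 10.4.3.6 specifies no liver-injury analysis, so the SAP adds one. Section 6.4.1 is a withholding rule for individual subjects that includes a clinical judgement, and nothing says that a summary table must use the same definition.

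The mechanism is not quantified. The bone-specific ALP evidence comes from adults, describes a transient rise and gives no size. The documents do not say whether the ALP reference limit is age-specific. If it is, normal growth is already allowed for, although the disease and the drug effect are not.

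Finally, replacing the SAP definition outright would not reproduce section 6.4.1, because a laboratory screen omits the judgement about other causes and the baseline condition. This objection stands and favours adding a row over substituting one.

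Together these arguments limit the consequence and the remedy. They do not remove the inconsistency: the evaluation that the SAP presents as its assessment of drug-induced liver injury can return zero when a subject met the protocol's laboratory criteria.

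**Conclusion.** The point holds as a possible under-count in one evaluation. By definition, a subject with ALP at or above 2x ULN throughout the window, or one who qualifies only through INR, cannot be counted under SAP section 9.6.6 but can meet the laboratory criteria of protocol section 6.4.1. Seven of the nine qualifying combinations are affected, four through ALP and three through INR, on the assumptions in Step 1.

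How often this would happen cannot be estimated. It depends on baseline ALP, the bone share of ALP, the size of the drug effect in children and the reference limits used, none of which the documents give. Few or no liver events are expected in 16 to 24 subjects, and any that occur should be visible as serious adverse events. This is an inexpensive improvement to the analysis definition and does not amount to a gap in the trial's safety surveillance.

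**What to change.** In SAP section 9.6.6 keep the Hy's Law row as it is. Beside it add a count by cohort and a subject listing of AST or ALT > 3x ULN with total bilirubin > 2x ULN, or INR > 1.5 where it was measured, regardless of ALP and within the same 7-day window. For each flagged subject show ALP at baseline and at the event, so that a reader can judge whether bone or liver is the likely source. State that INR comes from the Appendix A work-up and is not a scheduled test.

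The cost is a sentence or two in the SAP and one short listing, from data already collected. The downside is that a flagged subject may need individual review for cholestasis or another cause, a question that section 6.4.1 already raises. Only the analysis definition changes; no treatment-withholding rule is altered.

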9.6.7 Anti-romosuzomab Antibodies

Immunogenic response during the study will be described by tabulating the numbers and percentages of subjects who tested positive for (binding and neutralizing) anti-romosuzomab antibodies based on the safety analysis set.

9.6.8 Exposure to Investigational Product

Subject listing of manufacturing lot numbers and a separate listing of unique manufacturing lot numbers used in this study will be provided. Details for each romosuzomab administration will be listed for every subject.

Descriptive statistics will be produced to describe the exposure to IP by cohort.

10. Changes From Protocol-specified Analyses

According to Section 10.4.3.6 in protocol version superseding amendment 3 dated 28 February 2023, shifts in laboratory parameters between baseline and the most extreme post baseline values will be assessed base on the Severity Intensity Scale for Adverse Events. However, the laboratory abnormality with clinical significance is considered as adverse event. Therefore, the grade shifts in laboratory parameters will not be conducted.

11. Literature Citations / References

12. Appendices

Appendix A. Technical Detail and Supplemental Information Regarding Statistical Procedures and Programs

For the baseline assessment (excluding DXA), regardless of the width of the visit window, if there are multiple records within a Baseline window, the record that is the closest to and on or prior to Study Day 1 will be considered as the baseline value.

For the post-baseline assessment, if more than 1 visit falls within the defined window, the result from the visit closest to the target day will be used. If 2 evaluations are of the same distance from the target day, the result from the later visit will be used. If more than one evaluation on the same date, the average of the results will be used. Only laboratory results collected from the central laboratory will be averaged in the case of duplicate results.

To allow for variations in scheduling, the following visit windows will be used to assign evaluations to a most appropriate nominal visit for analysis and summarization. Furthermore, there will be no gaps between visit windows in order to include as many data points as possible for summarization.

Nominal Visit	Target Day	Window Definition (Study Day)
Baseline ^a	1	Last evaluation prior to or on Study Day 1
Day 85	85	Study Day 2 to 127
EOS	169	Study Day 128 to End of Study

Spine DXA Scans

^aIf results from baseline DXA are not available, the results from scans taken on or before Study Day 14 will be considered baseline values and not the Day 85 values.

Physical Examination and Facial Nerve Examination

Nominal Visit	Target Day	Window Definition (Study Day)
Baseline ^a	1	Last ealuation prior to or on Study Day 1
Day 57	57	Study Day 2 to 71
Day 85	85	Study Day 72 to 127
EOS	169	Study Day 128 to End of Study

^aAny assessment done on Study Day 1 but after the administration of the investigational product will be classified into Day 57.

12-lead ECG

Nominal Visit	Target Day	Window Definition (Study Day)
Baseline ^a	1	Last evaluation prior to Study Day 1
Day 8	8	Study Day 2 to 18

Day 29	29	Study Day 19 to 99
EOS	169	Study Day 100 to End of Study

^aAny assessment done on Study Day 1 but after the administration of the investigational product will be classified into **Day 8**

Laboratory Assessments (Chemistry)

Nominal Visit	Target Day	Window Definition (Study Day)
Baseline ^a	1	Last evaluation prior to or on Study Day 1
Day 8	8	Study Day 2 to 18
Day 29	29	Study Day 19 to 43
Day 57	57	Study Day 44 to 60
Day 64	64	Study Day 61 to 74
Day 85	85	Study Day 75 to 99
Day 113	113	Study Day 100 to 141
EOS	169	Study Day 142 to End of Study

^aAny assessment done on Study Day 1 but after the administration of the investigational product will be classified into Day 8.

Laboratory	Assessments	(iPTH)
------------	-------------	--------

Nominal Visit	Target Day	Window Definition (Study Day)
Baseline ^a	1	Last evaluation prior to or on Study Day 1
Day 8	8	Study Day 2 to 18
Day 29	29	Study Day 19 to 43
Day 57	57	Study Day 44 to 71
Day 85	85	Study Day 72 to 99
Day 113	113	Study Day 100 to 141
EOS	169	Study Day 142 to End of Study

^aAny assessment done on Study Day 1 but after the administration of the investigational product will be classified into Day 8.

Laborator	y Assessments	(Hematology)
-----------	---------------	--------------

Nominal Visit	Target Day	Window Definition (Study Day)
Baseline ^a	1	Last evaluation prior to or on Study Day 1
Day 29	29	Study Day 2 to 43
Day 57	57	Study Day 44 to 71
Day 85	85	Study Day 72 to 127
EOS	169	Study Day 128 to End of Study

^aAny assessment done on Study Day 1 but after the administration of the investigational product will be classified into Day 29.

Weight

Nominal Visit	Target Day	Window Definition (Study Day)
Baseline ^a	1	Last evaluation prior to or on Study Day 1
Day 29	29	Study Day 2 to 43
Day 57	57	Study Day 44 to 113
EOS	169	Study Day 114 to End of Study

^aAny assessment done on Study Day 1 but after the administration of the investigational product will be classified into Day 29.

Height

Nominal Visit	Target Day	Window Definition (Study Day)
Baseline ^a	1	Last evaluation prior to or on Study Day 1
EOS	169	Study Day 2 to End of Study

^aAny assessment done on Study Day 1 but after the administration of the investigational product will be classified into Day 169.

Vital Signs

Nominal Visit	Target Day	Window Definition (Study Day)			
Baseline ^a	1	Last evaluation prior to or on Study Day 1			
Day 29	29	Study Day 2 to 43			
Day 57	57	Study Day 44 to 60			
Day 64	64	Study Day 61 to 67			
Day 71	71	Study Day 68 to 78			
Day 85	85	Study Day 79 to 99			
Day 113	113	Study Day 100 to 141			
EOS	169	Study Day 142 to End of Study			

^aAny assessment done on Study Day 1 but after the administration of the investigational product will be classified into Day 29.

Serum PK and BTMs (sCTX and P1NP)

Nominal Visit	Target Day	Window Definition (Study Day)
Baseline ^a	1	Last evaluation prior to or on Study Day 1
Day 8	8	Study Day 2 to 11
Day 15	15	Study Day 12 to 22
Day 29	29	Study Day 23 to 43
Day 57	57	Study Day 44 to 60
Day 64	64	Study Day 61 to 67
Day 71	71	Study Day 68 to 78
Day 85	85	Study Day 79 to 99
Day 113	113	Study Day 100 to 141
EOS	169	Study Day 142 to End of Study

^aAny assessment done on Study Day 1 but after the administration of the investigational product will be classified into Day 8.

Antiromosozumab Antibody Assessments

Nominal Visit	Target Day	Window Definition (Study Day)			
Baseline ^a	1	Last evaluation prior to or on Study Day 1			
Day 15	15	Study Day 2 to 22			
Day 29	29	Study Day 23 to 57			
Day 85	85	Study Day 58 to 127			
EOS	169	Study Day 128 to End of Study			

^aAny antibody assessment done on Study Day 1 but after the administration of the investigational product will be classified into Day 15.

CONFIDENTIAL

Appendix B. Handling of Dates, Incomplete Dates and Missing Dates Imputation Rules for Partial or Missing Start Dates

		Stop Date							
		Complete: yyyymmdd		Partial: yyyymm		Partial: yyyy		Missing	
Start Date		< 1 st dose	≥ 1 st dose	< 1 st dose yyyymm	≥ 1 st dose yyyymm	< 1 st dose	≥ 1 st dose		
						уууу	уууу		
	= 1 st dose		1	n/a	1	n/a	1	1	
Partial:	уууутт	2							
уууутт	≠ 1 st dose		2	2	2	2	2	2	
	уууутт								
Partial:	= 1 st dose		1		1	n/a	1	1	
уууу	уууу	3		3					
	≠ 1 st dose		3		3	3	3	3	
	уууу								
Missing		4	1	4	1	4	1	1	

The reference date for the following rules is the date of first dose of study drug.

1=Impute the date of first dose; 2=Impute the first of the month; 3=Impute January 1 of the year; 4=Impute January 1 of the stop year

Note: For subjects who were never treated (first dose date is missing), partial start dates will be set to the first day of the partial month or first day of year if month is also missing.

Imputation Rules for Partial or Missing Death Dates

Incomplete or missing death dates will not be imputed.
